5.7.2 Smoking

Smoking will not be permitted on days of study drug administration until after lunch, and for 1 hour before each BP and pulse rate measurement outside these periods. Patients will otherwise be permitted to smoke their normal daily number of cigarettes.

5.7.3 Exercise

Patients are required to refrain from strenuous exercise from the screening visit until the final Follow-up Visit and will otherwise maintain their normal level of physical activity during this time (i.e., will not begin a new exercise program nor participate in any unusually strenuous physical exertion).

5.7.4 Blood Donation

Patients are required to refrain from donation until 3 months after the final Follow-up Visit.

5.7.5 Contraception

Female patients who are of non-childbearing potential will not be required to use contraception. Women of non-childbearing potential are defined as permanently sterile (i.e., due to hysterectomy, bilateral salpingectomy, or bilateral oophorectomy) or postmenopausal (defined as at least 1-year post cessation of menses without an alternative medical cause). Postmenopausal status will be confirmed with a screening serum FSH level >40 mIU/mL. FSH testing will be conducted in all postmenopausal females who are not surgically sterile regardless of age. Women aged >60 years whose FSH values are not >40 mIU/mL may be included at the discretion of the Investigator and in consultation with the Sponsor.

Female patients of childbearing potential must be willing to use a highly effective method of birth control (i.e., contraceptive measure with a failure rate of <1% per year) in conjunction with male barrier contraception (i.e., male condom with spermicide) from the time of signing the ICF until 30 days after the last dose of study drug. Highly effective methods of contraception include the following:

- Intrauterine device (IUD; e.g., Mirena®). Steel or copper IUDs are acceptable.
- Established use of oral, implanted, transdermal, or injectable hormonal method of contraception associated with inhibition of ovulation.
- Male sterilization (performed at least 90 days prior to the Screening Visit), with verbal confirmation of surgical success (for female patients on the study, the vasectomized male partner should be the sole partner for that patient).
- Bilateral tubal ligation or occlusion (performed at least 90 days prior to the Screening Visit).

Male patients with partners of childbearing potential must use a male barrier method of contraception (i.e., male condom with spermicide) in addition to a second method of acceptable contraception used by their female partners, from Day 1 until 90 days after the last dose of study drug. In addition to the list of highly effective contraception methods above, other acceptable methods of contraception for the female partner include the following:

- Established use of progesterone-only oral contraception, where inhibition of ovulation is not the primary mode of action.
- Diaphragm, cap, or sponge in conjunction with spermicide.

For male patients, sexual intercourse with female partners who are pregnant or breastfeeding should be avoided unless condoms are used from the time of the first dose until 90 days after the last dose of study drug. Male patients are required to refrain from donation of sperm from Day 1 until 90 days after the last dose of study drug.

Patients who practice true abstinence, because of the patient's lifestyle choice (i.e., the patient should not become abstinent just for the purpose of study participation) are exempt from contraceptive requirements. Periodic abstinence (e.g., calendar, ovulation, symptothermal, post ovulation methods) and withdrawal are not acceptable methods of contraception. If a patient who is abstinent at the time of signing the ICF becomes sexually active they must agree to use contraception as described previously.

For patients who are exclusively in same sex relationships, contraceptive requirements do not apply. If a patient who is in a same sex relationship at the time of signing the ICF becomes engaged in a heterosexual relationship, they must agree to use contraception as previously described.

The contraceptive method(s) being employed by patients should be reviewed with the patient during the course of the trial.

6 STUDY PROCEDURES

6.1 Screening Visit (Up to Day -21)

The following procedures will be performed at the Screening Visit:

- Obtain informed consent.
- Review inclusion/exclusion criteria.
- Record medical/surgical history and demographics.
- Perform full physical examination
- Record vital signs, height and weight (height will only be collected at the screening visit).
- Collect urinalysis assessment.
- Perform serum pregnancy test.
- Perform FSH testing.
- Collect blood samples for clinical safety chemistry panel, coagulation, and hematology assessments.
- Collect blood samples for TSH, HbA1c, and serology measurements.
- Collect blood samples for drugs of abuse.
- Collect blood for fasting lipid panel assessment.
- Perform 12-lead ECG measurements.
- Record adverse events.
- Record concomitant medications.

6.2 Treatment Period (Days 1 to 29)

6.2.1 Day 1

The following procedures will be performed at Day 1:

- Perform symptom-directed physical examination.
- Record vital signs and weight.
- Collect urine sample for urinalysis assessment.
- Perform urine pregnancy test.
- Collect blood samples for clinical safety chemistry panel, coagulation, and hematology assessments.
- Collect blood samples for fasting lipid panel assessment and statin PK.
- Collect blood samples for fasting apolipoproteins and LDL-C (beta-quant).
- Collect blood samples for hsCRP, PCSK9, and fibrinogen analysis.

- Collect blood samples for anti-drug antibody analysis
- Perform 12-lead ECG measurements.
- Randomize patients.
- Administer study drug.
- Collect blood samples for sparse PK, cytokine panel and complement activation analysis.
- Record adverse events including injection site reactions.
- Record concomitant medications.

6.2.2 Day 8

The following procedures will be performed at Day 8:

- Perform symptom-directed physical examination.
- Record vital signs and weight.
- Collect urine sample for urinalysis assessment.
- Perform urine pregnancy test.
- Collect blood samples for clinical safety chemistry panel, coagulation, and hematology assessments.
- Collect blood samples for fasting lipid panel assessment.
- Collect blood samples for fasting apolipoproteins and LDL-C (beta-quant).
- Collect blood samples for hsCRP, PCSK9, and fibrinogen analysis.
- Collect blood samples for sparse PK, cytokine panel and complement activation analysis.
- Record adverse events.
- Record concomitant medications.

6.2.2 Day 15

The following procedures will be performed at Day 15:

- Perform symptom-directed physical examination.
- Record vital signs and weight.
- Collect urine sample for urinalysis assessment.
- Perform urine pregnancy test.
- Collect blood samples for clinical safety chemistry panel, coagulation, and hematology assessments.
- Collect blood samples for fasting lipid panel assessment.
- Collect blood samples for fasting apolipoproteins and LDL-C (beta-quant).
- Collect blood samples for hsCRP, PCSK9, and fibrinogen analysis.

- Collect blood samples for anti-drug antibody analysis
- Collect blood samples for sparse PK, cytokine panel and complement activation analysis.
- Perform 12-lead ECG measurements.
- Record adverse events.
- Record concomitant medications.

6.2.3 Day 22

The following procedures will be performed at Day 22:

- Perform symptom-directed physical examination.
- Record vital signs and weight.
- Collect urine sample for urinalysis assessment.
- Perform urine pregnancy test.
- Collect blood samples for clinical safety chemistry panel, coagulation, and hematology assessments.
- Collect blood samples for fasting lipid panel assessment.
- Collect blood samples for hsCRP, PCSK9, and fibrinogen analysis.
- Collect blood samples for sparse PK, cytokine panel and complement activation analysis.
- Record adverse events.
- Record concomitant medications.

6.2.4 Day 29

The following procedures will be performed at Day 29:

- Perform symptom-directed physical examination.
- Record vital signs and weight.
- Collect urine sample for urinalysis assessment.
- Perform urine pregnancy test.
- Collect blood samples for clinical safety chemistry panel, coagulation, and hematology assessments.
- Collect blood samples for fasting lipid panel assessment and statin PK.
- Collect blood samples for fasting apolipoproteins and LDL-C (beta-quant).
- Collect blood samples for hsCRP, PCSK9, and fibringen analysis.
- Determine eligibility to receive 2nd study drug injection.
- Administer study drug.
- Collect blood samples for sparse PK, cytokine panel and complement activation analysis.

- Collect blood samples for anti-drug antibody analysis.
- Perform 12-lead ECG measurements.
- Record adverse events including injection site reactions.
- Record concomitant medications.

6.3 Follow-Up Period (Days 30 to 85 or End of Treatment)

6.3.1 Day 36

The following procedures will be performed at Day 36:

- Perform symptom-directed physical examination.
- Record vital signs and weight.
- Collect urine sample for urinalysis assessment.
- Perform urine pregnancy test.
- Collect blood samples for clinical safety chemistry panel, coagulation, and hematology assessments.
- Collect blood samples for fasting lipid panel assessment.
- Collect blood samples for hsCRP, PCSK9, and fibrinogen analysis.
- Collect blood samples for sparse PK, cytokine panel and complement activation analysis.
- Record adverse events.
- Record concomitant medications.

6.3.2 Day 43

The following procedures will be performed at Day 43:

- Perform symptom-directed physical examination.
- Record vital signs and weight.
- Collect urine sample for urinalysis assessment.
- Perform urine pregnancy test.
- Collect blood samples for clinical safety chemistry panel, coagulation, and hematology assessments.
- Collect blood samples for fasting lipid panel assessment.
- Collect blood samples for hsCRP, PCSK9, and fibrinogen analysis.
- Collect blood samples for anti-drug antibody analysis
- Collect blood samples for sparse PK, cytokine panel and complement activation analysis.
- Record adverse events.

Record concomitant medications.

6.3.3 Day 57

The following procedures will be performed at Day 57:

- Perform symptom-directed physical examination.
- Record vital signs and weight.
- Collect urine sample for urinalysis assessment.
- Perform urine pregnancy test.
- Collect blood samples for clinical safety chemistry panel, coagulation, and hematology assessments.
- Collect blood samples for fasting lipid panel assessment and statin PK.
- Collect blood samples for fasting apolipoproteins and LDL-C (beta-quant).
- Collect blood samples for hsCRP, PCSK9, and fibrinogen analysis.
- Collect blood samples for anti-drug antibody analysis
- Collect blood samples for sparse PK, cytokine panel and complement activation analysis.
- Perform 12-lead ECG measurements.
- Record adverse events.
- Record concomitant medications.

6.3.4 Day 85 or Early Termination

The following procedures will be performed at Day 85 or early termination:

- Perform full physical examination.
- Record vital signs and weight.
- Collect urine urinalysis assessment.
- Perform urine pregnancy test.
- Collect blood samples for clinical safety chemistry panel, coagulation, and hematology assessments.
- Collect blood samples for fasting lipid panel assessment.
- Collect blood samples for fasting apolipoproteins and LDL-C (beta-quant).
- Collect blood samples for hsCRP, PCSK9, and fibrinogen analysis.
- Collect blood samples for anti-drug antibody analysis
- Collect blood samples for sparse PK, cytokine panel and complement activation analysis.
- Perform 12-lead ECG measurements
- Record adverse events.

Record concomitant medications.

Extended Follow-up Visits

Extended follow-up visits will be conducted based on either LDL-C level at Day 85 or for safety considerations at the Investigator's discretion.

- If Day 85 LDL-C levels are <80% of their baseline level; extended follow-up will occur monthly for 3 months and end earlier if LDL-C levels are ≥80% of baseline. The fasting lipid panel will be assessed and occur monthly for up to 3 months or until LDL-C returns to within 80% of its baseline level (whichever is sooner). Those visits will also record AEs and concomitant medication.
- Extended Follow-up visits for safety considerations (frequency and assessments will be at the discretion of the Investigator) to monitor Investigator determined safety considerations may also occur and extend beyond 3 months, if deemed appropriate by the Investigator, and will continue until there are no safety observations requiring further follow-up. Those visits will also record AEs and concomitant medication.

For extended follow-up Visits due to LDL-C <80% of the baseline level. The procedures need to be performed will include the following:

- Record vital signs and weight.
- Collect blood samples for fasting lipid panel assessment.
- Record adverse events.
- Record concomitant medications.

For extended follow-up Visits for safety considerations, the procedures need to be performed will be consideration specific and may include but not be limited to the following:

- Record vital signs and weight.
- Collect urine sample for urinalysis assessment.
- Collect blood samples for clinical safety chemistry panel, coagulation, and hematology assessments.
- Perform 12-lead ECG measurements.
- Record adverse events.
- Record concomitant medications.

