3.2 Study Design Rationale

Based on initial data from the ongoing FIH study and within the context of a limited experience, CIVI 007 appears to provide the expected pharmacologic profile associated with PCSK9 inhibition. CIVI 007 shows PCSK9 knockdown that begins around 12.5 mg with maximal inhibition of approximately 90% at common mg. The efficacy profile includes robust, dose-dependent reductions in atherogenic lipoproteins and lipids that appear to peak within a week following administration and are stable out to 4 weeks after administration. Changes in lipoproteins and lipids after multiple doses are consistent with those after single doses.

CIVI 007 therefore appears to have a favorable clinical profile and justify advancement to Phase 2 testing in this study. The Phase 2a study will provide robust information to determine advancement of the program to Phase 2b/3 testing. A forced up-titration dosing group (cc) mg) will provide an initial understanding of this dosing strategy on CIVI 007's clinical profile.

A parallel group design, as opposed to an ascending dose design, has been chosen as initial Phase 1 observations have demonstrated safety in the study dose range. Subcutaneous dosing has been chosen as this is the intended clinical route of administration.

Dosing and follow-up will occur in a double-blind state for the Investigator and clinical staff in order to avoid bias in the collection of data.

Conducting the study in patients with LDL-C levels in the study range and on a background of a stable dose of statin therapy (with or without ezetimibe) will enable safety, tolerability, PK, and PD data to be collected in the intended clinical population in whom additional drug treatment may be warranted to optimize their LDL-C levels.

Placebo has been chosen as the control treatment to assess whether any observed effects are treatment-related or simply reflect the study conditions.

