5.3 Randomization and Blinding

Approximately 48 patients will be assigned randomly to placebo, comma CIVI 007, comma CIVI 007 followed by comma CIVI 007 or comma CIVI 007 in a 1:1:1:1 allocation ratio.

Throughout the study, study treatment will be administered in a double-blinded fashion for the Investigator, clinical staff, and patients. Only where required will key site staff (such as pharmacist) be unblinded throughout the study.

The following controls will be employed to maintain the double-blind execution of the study:

• The placebo solution will be identical in appearance to the CIVI 007 solution.

- The Investigator and other members of staff involved with the study will remain blinded.
- Lipid levels after randomization will be blinded to the study site.
- Appropriate firewalls will exist to prevent communication between the unblinded SRC and personnel involved in study execution.

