7 EFFICACY ASSESSMENTS

7.1 Primary Endpoints

The primary safety/tolerability endpoints for this study are as follows:

- incidence and severity of any drug-related AE
- incidence of clinically significant laboratory abnormalities, based on drug-induced changes from baseline in hematology, clinical safety chemistry, and urinalysis test results.

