8.2 Adverse Events

An adverse event is defined as any untoward medical occurrence in a clinical investigation patient administered a pharmaceutical product, which does not necessarily have a causal relationship with this treatment. An adverse event can therefore be any unfavorable and/or unintended sign (including an abnormal laboratory finding), symptom, or disease temporally associated with the use of an IMP, whether or not related to the IMP. All adverse events, including observed or volunteered problems, complaints, or symptoms, are to be recorded on the appropriate eCRF.

Adverse events, which include clinical laboratory test variables, will be monitored and documented from the time of screening until completion of the Day 85 Visit, early termination visit or extended Follow-up, whichever is later. Patients should be instructed to report any adverse event that they experience to the Investigator, whether or not they think the event is due to study treatment. Beginning at screening, Investigators should make an assessment for adverse events at each visit and record the event on the appropriate adverse event eCRF.

Wherever possible, a specific disease or syndrome rather than individual associated signs and symptoms should be identified by the Investigator and recorded on the eCRF. However, if an observed or reported sign or symptom is not considered a component of a specific disease or syndrome by the Investigator, it should be recorded as a separate adverse event on the eCRF. Additionally, the condition that led to a medical or surgical procedure (e.g., surgery, endoscopy, tooth extraction, or transfusion) should be recorded as an adverse event, not the procedure itself.

Any medical condition already present at Screening, should be recorded as medical history and not be reported as an adverse event unless the medical condition or signs or symptoms present at baseline changes in severity, frequency, or seriousness at any time during the study. In this case, it should be reported as an adverse event.

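### The LDL-C-triggered extension tells a lipid-blinded Investigator that Day 85 LDL-C is still more than 20% below baseline, which can bias causality of AEs that start, stay open or are re-assessed after that result

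*Protocol*

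**What the plan says.** **Blinding.** Protocol Section 5.3 (repeated in SAP Section 2.2.2) lists among its controls: "Lipid levels after randomization will be blinded to the study site", and "The Investigator and other members of staff involved with the study will remain blinded". Neither has an end date or an exception. Section 3.2 extends the principle past dosing: "Dosing and follow-up will occur in a double-blind state for the Investigator and clinical staff in order to avoid bias". The one firewall described concerns the Safety Review Committee.

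**Extension.** The Extended Follow-up Visits text, after Protocol Section 6.3.4, gives two routes.

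- The lipid route: "If Day 85 LDL-C levels are <80% of their baseline level; extended follow-up will occur monthly for 3 months and end earlier", that is, once a patient is back to at least 80% of baseline. It adds: "The fasting lipid panel will be assessed and occur monthly for up to 3 months or until LDL-C returns to within 80% of its baseline". Its visits have their own procedure list, introduced by the words "For extended follow-up Visits due to LDL-C <80% of the baseline level".
- The safety route, at the Investigator's discretion.

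The synopsis, Section 3.1, Appendix A and SAP Section 2.2.1 also carry the lipid rule. None says who applies it or how the site is told.

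**Adverse events.** Section 8.2 collects AEs "until completion of the Day 85 Visit, early termination visit or extended Follow-up, whichever is later", and both kinds of extension visit record them. Under Section 8.2.3 the Investigator classifies each AE as related to study drug, yes or no. That classification defines the first primary endpoint in Section 7.1: "incidence and severity of any drug-related AE".

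**The concern.** The site is kept from lipid results so that it cannot infer treatment from the drug's main pharmacodynamic effect. The extension rule then hands over a dichotomised version of the same result. The Investigator starts every safety-driven extension, so any extension not started by the Investigator must come from LDL-C. The month in which it ends gives a second piece of lipid information.

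If LDL-C lowering persists to Day 85, extended patients will mostly be on active drug. An Investigator who knows this could more readily call an AE related in an extended patient, or unrelated in one who was released. The judgment at risk is the one that defines a primary endpoint. With 12 patients per group and a descriptive safety analysis, a few differently classified AEs would be visible in the table.

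**Working it through.** The plan gives no expected number of patients in extension and no expected Day 85 effect, so there is no stated figure to reproduce. The calculation asks how much the call tells the Investigator.

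**Inputs from the documents**

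- Allocation 1:1:1:1, about 48 patients (Protocol Sections 5.1 and 9.2.4): 48/4 = 12 per group, so P(active) before any call = 36/48 = 0.75.
- Trigger: LDL-C below 80% of baseline, a percent change below −20.
- Timing: Day 85 is 85 − 29 = 56 days after the last dose.
- Persistence: the human lipid effect is described as stable to 4 weeks only (Sections 3.2 and 5.2). In monkeys, PCSK9 had not fully returned in the 8-week recovery phase, nor apoB in 7 weeks (Section 1.2.1).

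**Assumptions, not in the documents**

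- Day 85 percent change in LDL-C is normal, with the same SD (10 to 25 points) in placebo and active.
- Placebo mean is 0. The active groups share one mean residual lowering of 0, 10, 20 or 30%.

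**Formulas**

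- P(call) = Φ((−20 − mean)/SD), written p0 for placebo and p1 for active.
- P(active | called) = 0.75·p1 / (0.75·p1 + 0.25·p0).

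Placebo: p0 = Φ(−20/SD) = 0.023, 0.091, 0.159, 0.212 for SD 10, 15, 20, 25.

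Worked case, residual lowering 30% and SD 15: p1 = Φ(10/15) = 0.748. P(active | called) = 0.75 × 0.748 / (0.75 × 0.748 + 0.25 × 0.091) = 0.561/0.584 = 0.961. Expected calls: 36 × 0.748 ≈ 27 active and 12 × 0.091 ≈ 1 placebo.

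P(active | called):

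| Residual lowering at Day 85 | SD 10 | SD 15 | SD 20 | SD 25 |
|---|---|---|---|---|
| 0% | 0.750 | 0.750 | 0.750 | 0.750 |
| 10% | 0.954 | 0.893 | 0.854 | 0.830 |
| 20% | 0.985 | 0.943 | 0.904 | 0.876 |
| 30% | 0.991 | 0.961 | 0.929 | 0.903 |

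Release without extension is informative too. At 30% and SD 15, P(placebo | not called) = 0.25 × 0.909 / (0.25 × 0.909 + 0.75 × 0.252) ≈ 0.55, against 0.25 beforehand. At 10% residual lowering it is only 0.28 to 0.29.

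**Which data are exposed.** The signal cannot exist before the Day 85 result. Both doses and all scheduled visits precede it, and Section 8.2 asks for AE assessment at each visit. What remains is an AE that starts in extension, is still open when the call arrives, or is re-assessed afterwards. LDL-C-triggered visits collect vital signs, weight, fasting lipids, AEs and concomitant medication. They include no safety chemistry, hematology or urinalysis, so they supply no laboratory data for the second primary endpoint.

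**The case against.** The strongest reply is that this is late and small.

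- **Narrow window.** Most AE causality should already be entered before the Day 85 LDL-C result exists, and patients who are not extended have finished AE collection. This stands, and it sets the scope of the point.
- **Unknown strength.** The documents give no human lipid effect 8 weeks after a dose. A placebo patient can also fall by more than 20% through ordinary variability or a background-therapy change, which is allowed when medically necessary (Section 5.6.2) and does not lead to withdrawal (Section 4.5). This stands: the signal is probabilistic and vanishes if the effect has gone.
- **Limited consequence.** Safety analysis is descriptive (Section 9.2.1), and SAP Section 3.6.1 also tabulates all AEs regardless of relatedness. This softens the effect but does not protect the endpoint, which is drug-related AEs.
- **The site cannot apply the rule.** Because it does not see lipids, someone else presumably does. That does not close the gap, because the call itself carries the result.
- **Operational documents may mask the trigger.** They may, but neither the protocol nor the SAP contains or refers to such a step.

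A reader might infer that Section 8.2 lets causality be revised during extension. It does not say so; it sets the collection window. The nearest support is SAP Section 3.6.1, whose treatment-emergent definition includes AEs whose relationship to drug worsens, which implies that the classification can change.

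**Conclusion.** The conflict is in the text. The site is blinded to post-randomization lipids, yet it must run separately labelled visits because of one, while Investigator causality still feeds a primary endpoint. If LDL-C lowering of 10–30% remains at Day 85, being called moves the probability of active treatment from 75% to roughly 83–99%, assuming a placebo mean of zero and an SD of 10–25 points in both groups. With no residual effect it stays at 75%.

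Two stronger readings are tempting and unsupported. One is that extension identifies active treatment. That requires a substantial effect 56 days after the last dose, which the documents do not report in humans. The other is that the drug-related AE endpoint as a whole is compromised. Only AEs that start, remain open or are re-assessed after the Day 85 result are exposed. The documents do not allow an estimate of how many that is, so the calculation measures how guessable treatment becomes, not the resulting bias. This is a real but modest late gap in the blind, and cheap to narrow.

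**What to change.** Leave the 80% threshold and the visit schedule unchanged.

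**Protocol** (Extended Follow-up Visits, with cross-references in Sections 5.3 and 8.2)

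1. State that the central laboratory or IRT, not the site, applies the rule and sends a reason-neutral message: *continue* or *complete*.
2. Release that message only after severity and causality of every AE with onset through the Day 85 visit are entered and signed in EDC.
3. State that safety-driven extension and SAE reporting are not delayed.

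**SAP Section 3.6.1**

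4. Summarise drug-related AEs with onset through Day 85 separately from those starting in LDL-C-triggered extension. This also shows the effect of the longer AE observation in patients with persistent lowering.
5. List any causality changed after release, and add a sensitivity summary using the pre-release assessments. Later updates stay allowed, because Section 8.4 requires SAE follow-up. The audit trail in Section 10.1.1 already captures the changes, so no new system is needed.

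**Cost.** A release rule in IRT/EDC, some protocol and SAP wording, and a few days' wait for AE sign-off before the extension call. The wait is tolerable because extension visits are monthly.

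**Limit.** Neutral wording cannot hide the reason from an Investigator who knows that the extension was not self-initiated. The change protects assessments through Day 85 and makes the rest visible; it does not blind AEs that start during extension.
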